7.5 Follow up for Adverse Events

Upon completion of the study imaging, subjects will be contacted to screen for adverse events after a period of 2 and 30 days from procedure. Patients with abnormal laboratory or clinical findings will be followed until the condition resolves or stabilizes, or until the laboratory values are no longer considered clinically significant. Adverse events or serious adverse events that occur during the follow-up period will be recorded regardless of relatedness to the study procedure. The safety follow-up may be conducted by a phone call or a clinic visit; if clinically indicated, a clinic visit should be performed along with relevant lab work.

Patients will be contacted via phone at 1- and 2-years post-appointment for follow up evaluation. See MOP for further details.

7.6 Safety Monitoring

100% of serious adverse events will be monitored by the PI and study team. Because this is a low risk study there is no Data Safety Monitoring Board. Adverse events will be reviewed annually by the IRB. Serious adverse events will be reported within 5 days by the PI to IRB. Any event that is reportable to the IRB will also be reported to the DRC and FDA in accordance with their polices.

8. INTERVENTION DISCONTINUATION

N/A

9. STATISTICAL CONSIDERATIONS

9.1 General Design Issues

The primary outcome of this cross- sectional study is to measure the operating characteristics including SN, SP, PPV and NPV comparing the physician- and algorithm-guided HRME-based image compared to the Lugol's- guided physician diagnosis of HSIL during HRA.

9.2 Sample Size and Randomization

The study will primarily be powered to determine the precision around the operating characteristics of mHRME imaging. We estimate that because the median number of lesions per patient is approximately 1.5-2, and HSIL prevalence of 30%, approximately 150 patients (225-300) lesions will be needed to estimate the confidence intervals around SN and SP estimates see Table 1 below. In order for 150 patients to complete study procedures, we will target a total enrollment of 200, because we will also be improving the technology as a secondary objective and assume that up to 30% of patients may not have evaluable optimized HRME images.

Precision calculation

The damage to precision due to within-subject correlation is mitigated by the fact that the average number of per-patient slides is at most 2. Correlation = 0.5 is a high estimate, but the table below shows precision values close to the original independence-assumption based ones.

SN/SP estimate	¹ / ₂ width CI for 225 slides		¹ / ₂ width CI for 300 slides		
	indep	$\operatorname{corr} = 0.5$	indep	corr = 0.5	
10%	4.66%	6.99%	3.94%	5.91%	
15%	5.28%	7.93%	4.50%	6.75%	
20%	5.74%	8.61%	4.91%	7.37%	
25%	6.07%	9.10%	5.21%	7.82%	
30%	6.30%	9.46%	5.43%	8.14%	
35%	6.46%	9.69%	5.57%	8.35%	
40%	6.54%	9.81%	5.65%	8.47%	
45%	6.55%	9.82%	5.67%	8.50%	
50%	6.50%	9.74%	5.63%	8.45%	
55%	6.55%	9.82%	5.67%	8.50%	
60%	6.54%	9.81%	5.65%	8.47%	
65%	6.46%	9.69%	5.57%	8.35%	
70%	6.30%	9.46%	5.43%	8.14%	
75%	6.07%	9.10%	5.21%	7.82%	
80%	5.74%	8.61%	4.91%	7.37%	
85%	5.28%	7.93%	4.50%	6.75%	

Treatment Assignment Procedures

All participants will undergo HRME-imaging prior to biopsy

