Squamous cell cancer of the anus (SCCA) is one of the most common cancers among aging HIVinfected individuals in the United States. HIV-infected persons are at 40-80-times higher risk for SCCA than the general population, and recent cohort studies report that the incidence of SCCA among HIV-infected men is between 49-144/100,000 person-years, which is substantially higher than the incidence of cervical cancer prior to widespread screening with cervical cytology. The alarming increase in anal precancer and cancer in HIV- infected individuals has led to an increased emphasis on prevention. Current HIV primary care Guidelines (NY state HIV primary care guidelines, HIV Medical Association, and Infectious Diseases Society of America) both recommend annual anal cytology screening, with triage to high resolution anoscopy (HRA)-guided biopsy for histologic confirmation of anal high grade intraepithelial lesions (HSIL) among HIVinfected men who have sex with men (MSM), and certain HIV-infected women. However, HRAguided histologic diagnosis of HSIL is resource intensive, and has several drawbacks, including: extensive clinician expertise/training; pathology cost, availability, interpretation expertise; separate patient visits for diagnosis and treatment; and patient discomfort associated with unnecessary, non-neoplastic biopsies, given the low specificity of HRA-based visual HSIL identification. Our group has developed a portable, battery-operated, high-resolution microendoscope (mHRME) that provides subcellular images of the anal epithelium, delineating the cellular and morphologic changes associated with neoplasia. Our central hypothesis is that this 'optical' approach will increase the efficiency, clinical impact, and cost-effectiveness of the current standard of HRA-guided biopsy. In a recent pilot trial, the mHRME demonstrated a high sensitivity and specificity of anal HSIL diagnosis (94% and 92% respectively) compared to anal biopsy. Based on our significant preliminary data, we now propose to optimize and validate 3D imaging and HRME with a software interface that provides real- time image interpretation assistance, thus facilitating usage by less-experienced clinicians in community-based or low-resource settings. To validate this, we will conduct a study to determine the efficiency and diagnostic characteristics of an mHRME 'optical biopsy' approach versus the current standard of HRA-based tissue biopsy. In addition, we will construct, refine and analyze a disease model of HRA-based screening with mHRME to determine the cost- effectiveness of incorporating HRME into HRA-based HSIL diagnosis. Successful results will allow for improved efficacy and resource utilization for cancer screening in HIV-infected individuals for anal cancer and other epithelial cancers including the cervix, oral cavity, bladder, and GI tract.

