9.6 Data Analyses

Objective 1. We will determine the performance characteristics of mHRME for the prediction of anal HSIL in flat mucosa and mucosal lesions using histopathology as the gold standard. Our hypothesis is that the sensitivity (SN) specificity (SP), positive predictive value (PPV) and negative predictive value (NPV), as well as the receiver operating curve for the identification of neoplasia on a per biopsy and per patient basis will be high. We will first compare the HRA-directed biopsy (as the gold standard) to the results of the mHRME HSIL diagnosis. The SN of mHRME diagnosis in detection of HSIL will be estimated with the binomial proportion of study participants who are positive for HSIL on HRA-guided biopsy at two thresholds of histology thresholds which are: 1) AIN 2+ threshold, and 2) AIN3+ threshold. SP will be estimated as the proportion of study participants who are negative for HSIL on HRA-guided biopsy at both thresholds. Positive and negative predictive values will be estimated using the binomial proportion and its 95% CI. In addition, the Cohens kappa statistic, and receiver operator characteristic curves will be generated if patient characteristics such as low CD4 count, cART utilization, or high HIV viral load impact the determination of SN and SP. The lab information will be collected and placed in the source document and entered in Oncore. SN and SP of mHRME-based HSIL diagnosis will be estimated on a per lesion and per patient basis with 95% confidence intervals and compared by McNemar's test. A generalized linear model for logistic regression with multiple correlated outcomes will compare SN and SP of each method on a per biopsy and per patient basis. For Device optimization: No Data Analyses are planned.

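### The precision table counts every slide towards both sensitivity and specificity, so the stated precision for sensitivity is about twice as good as the design can deliver

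*Combined protocol and SAP*

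**What the plan says.** Section 9.2 takes as inputs that "the median number of lesions per patient is approximately 1.5-2, and HSIL prevalence of 30" per cent. From 150 evaluable patients and 1.5-2 lesions each it concludes that "approximately 150 patients (225-300) lesions will be needed to estimate the confidence intervals around SN and SP estimates see Table 1 below". A single table follows. Its row label covers SN and SP jointly, and its column headings (for example "width CI for 225 slides") give the total slide count. At 85% it prints half-widths of 5.28 and 4.50 points under independence, and 7.93 and 6.75 points with a within-patient correlation of 0.5.

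Section 9.6 defines the estimates differently: "The SN of mHRME diagnosis in detection of HSIL will be estimated with the binomial proportion of study participants who are positive for HSIL" on biopsy, with SP taken among those negative. Both are to be reported per lesion and per patient with 95% intervals. The opening summary reports that in a pilot "the mHRME demonstrated a high sensitivity and specificity of anal HSIL diagnosis (94% and 92% respectively"), and Section 2.1 cites preliminary values of 93% and 87%.

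**The concern.** A lesion is either HSIL or not, so it can enter the SN denominator or the SP denominator but never both. A table that uses all 225 or 300 slides for both measures gives each of them more data than it will have, and the rarer class suffers most. At 30% prevalence that class is HSIL, and so the affected measure is SN.

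Section 9.2 says the study is powered primarily on precision, and this table is the only quantitative support for 150 evaluable patients. SN also matters most for the stated purpose: if an optical read is to replace a biopsy, the question is how many HSIL lesions it would miss. A reader who expects about ±5 points at 85% will receive about ±9 to ±11.

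**Working it through.** **Inputs.** Total lesions N: 150 × 1.5 = 225 to 150 × 2 = 300 (Section 9.2). HSIL prevalence: 30% (Section 9.2), taken here as lesion-level, which the plan does not state. Confidence level: 95% (Section 9.6). Preliminary SN: 93% (Section 2.1).

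**Step 1: reproduce the printed table.** Take logit(p) ± 1.96/√(n·p·(1−p)), transform back, and report the longer arm. For p = 0.85 and n = 225:
- logit(0.85) = 1.7346.
- Margin = 1.96/√(225 × 0.1275) = 0.3659.
- Limits = 79.72% and 89.10%, so the longer arm is 85 − 79.72 = 5.28 points, as printed.
- With n = 300 the result is 4.50, as printed.

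All 32 independence cells (16 rows, two columns) are reproduced to two decimals. This works only with all slides as n, so prevalence did not enter.

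**Step 2: use the proper denominators.**
- SN: 0.3 × 225 = 67.5 to 0.3 × 300 = 90 lesions.
- SP: 0.7 × 225 = 157.5 to 0.7 × 300 = 210 lesions.

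For SN at 85% and n = 67.5, the margin is 1.96/√(67.5 × 0.1275) = 0.6681. The lower limit is 74.39%, so the half-width is 10.61 points.

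Half-widths in points, independence, for N = 225 / 300:

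| Assumed value | All slides (plan's method) | SN, HSIL lesions only | SP, non-HSIL lesions only |
|---|---|---|---|
| 85% | 5.28 / 4.50 | 10.61 / 8.94 | 6.46 / 5.49 |
| 90% | 4.66 / 3.94 | 9.75 / 8.12 | 5.75 / 4.85 |
| 93% | 4.16 / 3.50 | 9.09 / 7.47 | 5.19 / 4.34 |
| 95% | 3.75 / 3.13 | 8.59 / 6.96 | 4.73 / 3.92 |

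At 85% the SN ratio is 10.61/5.28 = 2.01 and 8.94/4.50 = 1.99, and the SP ratio is 1.22. The SN ratio is 1.8 at 50% and 2.1-2.2 at 93%.

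**Step 3: check with another interval.** For a simple Wald interval the ratio does not depend on p: 1/√0.3 = 1.83 for SN and 1/√0.7 = 1.20 for SP. At 85%, Wald SN is 8.52 against 4.67 (225 slides) and 7.38 against 4.04 (300 slides).

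**Step 4: vary the prevalence (SN at 85%, N = 225 / 300).** At 20%: 13.57 / 11.39, ratio about 2.5. At 40%: 8.94 / 7.56, ratio 1.7. At 50%: 7.84 / 6.65, ratio 1.5.

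**Step 5: correlation columns.** These equal 1.5 times the independence half-width. A design effect of 1 + (2−1) × 0.5 = 1.5 applies to the variance and would widen the interval by √1.5 = 1.22. With that design effect, SN has an effective n of 67.5/1.5 = 45 to 90/1.5 = 60. The half-widths are then 13.57 / 11.39, about 1.7 times the printed 7.93 / 6.75. With the plan's own factor of 1.5 they are 15.91 / 13.41.

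**Step 6: per patient.** If 30% is instead the patient-level figure, 150 × 0.3 = 45 patients have HSIL and 105 do not. By the table's method SN is 13.57 points at 85% and 12.13 at 93%, and SP is 8.17 at 85%.

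**Step 7: lesions needed for the printed SN precision.** 225/0.3 = 750 to 300/0.3 = 1000.

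**The case against.** - **Prevalence basis.** The plan does not say whether 30% is per lesion or per patient. Section 2.2 gives a similar figure (29.1%) as a per-person prevalence among HIV-infected MSM. Eligibility requires prior HSIL or abnormal cytology (Section 4.1), which could raise the lesion-level share. The normal-site biopsies in Section 5.1 would lower it if they are counted among the slides. This stands: 68-90 lesions is an assumption. It changes the size of the error, but SN precision is overstated throughout the 20-50% range.
- **Correlation columns.** They widen the interval more than a design effect of 1.5 would, which offsets part of the error. The offset is real but too small: the printed 7.93 and 6.75 are still narrower than the corrected SN values with no correlation at all (10.61 and 8.94).
- **Row range.** The table is symmetric, so its 10% row (4.66 / 3.94) also serves for 90%, and a final row may have been lost when the PDF was read. This stands: only values above 90% are clearly absent.
- **No criterion is breached.** The plan sets no target half-width and no performance goal for SN, and every imaged site is biopsied, so no participant's biopsy depends on this table. That is fair, and it is why enrolment need not change. It does not rescue a sample-size justification that is numerically wrong on the plan's own inputs.

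**Conclusion.** Wrong as written. The table describes the precision of a proportion estimated from all lesions, which is neither SN nor SP as Section 9.6 defines them. At 30% lesion-level prevalence the SN half-width is understated about twofold across the upper rows (1.8 at 50%, 2.0 at 85%), and the SP half-width by about 20%. The direction of the error does not depend on the interval method or on the correlation assumption. Its size depends on the lesion-level HSIL share, which the plan leaves open. The missing per-patient precision and the missing rows above 90% are lesser gaps in the same table.

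**What to change.** Replace the joint table in Section 9.2 with separate SN and SP columns: SN on 68-90 HSIL lesions and SP on 158-210 non-HSIL lesions, or the counts that follow from a justified lesion-level prevalence. In the same revision:
- State whether 30% is per lesion or per patient, and whether normal-site biopsies count towards the 225-300. Show SN precision over a range such as 20-50%.
- Include rows for 90% and 95%, so that the pilot values are covered.
- Add a per-patient line (45 HSIL and 105 non-HSIL patients if 30% applies per patient).
- Name the interval method, keep a correlation column, and say whether 1.5 multiplies the variance or the half-width.
- Reword the conclusion so that it states the precision actually expected.

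The cost is one table and one paragraph. The enrolment target can stay, provided the investigators accept an SN half-width of about 9-11 points at 85% before any allowance for correlation.

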5. STUDY INTERVENTIONS

5.1 Interventions, Administration, and Duration

Study Drug – Proflavine Hemisulfate

Proflavine was used under FDA IND #102217; the HRME itself is an IDE-exempt device by the FDA. The contrast agent, proflavine, used in this study is the principal component of acriflavine and has been used for fluorescent imaging in the European, Asian and Australian gastrointestinal literature without any adverse events.

Study Intervention - mobile High Resolution Microendoscope (mHRME)

Patients will have mHRME images taken of Lugol's negative (abnormal) areas and subsequent standard-of-care HRA biopsies at each image site. In addition, there will be at least one extra image and biopsy taken at a Lugol's positive (normal) site. Each patient will likely have ≥ 2 biopsies. We plan to enroll 200 patients, which will yield 225-300 images.

Our approach uses topical contrast (proflavine) that directly highlights cell nuclei change, the most important pathologic marker of squamous cell intraepithelial neoplasia. In addition, we will implement image-analysis software to highlight these changes in real time, enabling less experienced practitioners to accurately recognize the hallmarks of neoplasia. The high-resolution fiber-optic microendoscope (mHRME) proposed for use here delivers 0.5 mW of 455 nm light to the tissue through a 0.8 mm diameter fiber- optic bundle, corresponding to an irradiance level of 100mW/cm2.

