Objective 2a. Determine clinical efficiency of mHRME + HRA for the diagnosis of HSIL. Clinical efficiency is defined as: `Diagnostic Yield: Percent of HRME diagnosed HSIL lesions that were classified as non-HSIL by clinician. `Biopsies averted: Percent of HRAvisualized lesions that the clinician originally categorized as potentially needing a biopsy but on mHRME were appropriately down-graded, averting an unnecessary biopsy. Procedure time: Total procedure time (mHRME and HRA). For Diagnostic Yield and Biopsies Averted, we will estimate 95% confidence intervals. Total procedure time will be recorded. mHRME Procedure time will measured separately once mHRME is initiated. Median and standard deviation of procedure times and mHRME procedure times will be calculated.

Objective 2b. Images collected from the 50 patients will be compared to biopsies. Preliminary Sensitivity, Specificity, positive predictive value (PPV) and negative predictive values (NPV) will be estimated and precision of interval width calculations will be done.

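### At the plan's maximum 30% loss, enrolling 200 gives 140 evaluable patients, not 150; and Section 5.1's image count is the lesion count for 150 patients, without the normal sites

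*Combined protocol and SAP*

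**What the plan says.** **Enrolment (Section 9.2).** The precision calculation needs about 150 patients, giving 225–300 lesions, "because the median number of lesions per patient is approximately 1.5-2". The enrolment sentence reads "In order for 150 patients to complete study procedures, we will target a total enrollment of 200". Its reasons are that the technology will be improved during the study and that the investigators "assume that up to 30% of patients may not have evaluable optimized HRME images". The precision table that follows is computed for 225 and 300 slides, with the remark that "the average number of per-patient slides is at most 2".

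**Images (Section 5.1).** "We plan to enroll 200 patients, which will yield 225-300 images". The same paragraph requires images and biopsies of Lugol's-negative (abnormal) areas, and adds that "there will be at least one extra image and biopsy taken at" a Lugol's-positive (normal) site. It also says "Each patient will likely have ≥ 2 biopsies".

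**Analysis (Section 9.6).** Objective 1 covers flat as well as lesional mucosa. It speaks twice of a per-biopsy basis and once of a per-lesion basis for sensitivity and specificity. Under Objective 2b: "Images collected from the 50 patients will be compared to biopsies". No other section defines that group of 50.

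**Procedure (Appendix 1, Manual of Operations, step 19).** The steps go through abnormal areas only, first by HRA, then by HRME, then by biopsy. They do not mention a normal-site image or biopsy.

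**The concern.** An allowance for loss is normally sized at its stated maximum. Here the maximum loss and the enrolment do not return the stated target, so the table's slide counts are not secured under the plan's own assumption.

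Section 5.1 and Section 9.2 give the same range, 225–300, for two different things: images from 200 enrolled patients, and lesions from 150 patients. A reader cannot tell how many samples of each kind to expect.

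This bears on the primary outcome, because specificity and NPV are part of it. Normal-looking sites are biopsied by design and mostly add to the histology-negative group. A pooled figure and a lesion-only figure answer different questions. The efficiency claim, biopsies averted by down-grading lesions seen at HRA, depends on performance in visible lesions.

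**Working it through.** **Inputs.** Enrolment 200, target 150, loss up to 30%, 1.5–2 lesions per patient and 30% HSIL prevalence (Section 9.2); 225–300 images and at least one normal site per patient (Section 5.1).

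**1. The plan's lesion count.** 150 × 1.5 = 225 and 150 × 2 = 300. This reproduces exactly. It treats the median as a mean, as Section 9.2 does.

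**2. Enrolment.**
- Forward: 200 × (1 − 0.30) = 140, which is 10 short of 150.
- Backward: 150 / (1 − 0.30) = 214.3, so 215 would be needed at 30% loss.
- Break-even loss: (200 − 150) / 200 = 25%.
- Lesions from 140 patients: 140 × 1.5 = 210 and 140 × 2 = 280.

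**3. Precision cost of 140 against 150.** Half-width scales roughly with √(150/140) = 1.035. Applied to the 85% row of the plan's table:

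| Column | Plan | At 140 patients | Cost (points) |
|---|---|---|---|
| 225 slides, independent | 5.28 | 5.47 | 0.19 |
| 225 slides, corr = 0.5 | 7.93 | 8.21 | 0.28 |
| 300 slides, independent | 4.50 | 4.66 | 0.16 |
| 300 slides, corr = 0.5 | 6.75 | 6.99 | 0.24 |

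As a second check, take sensitivity at 85% on HSIL lesions only (30% of lesions, independence, Wilson interval). The half-width is 8.79 with 63 lesions against 8.50 with 67.5, and 7.62 with 84 against 7.37 with 90. These are not the plan's table figures, which use all slides as the denominator. The cost is again about 0.3 points.

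**4. Images.** One retained image per site is assumed, since the Manual has the best image of each site selected.
- As stated: 225/200 = 1.125 and 300/200 = 1.5 images per enrolled patient. After one normal-site image, 0.125–0.5 lesion images each would remain, against 1.5–2 in Section 9.2.
- At two biopsies each: 400 sites for 200 patients, 300 for 150, 280 for 140.
- Lesions plus one normal site (2.5–3 per patient): 140 × 2.5 = 350 to 140 × 3 = 420; 150 × 2.5 = 375 to 150 × 3 = 450.

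**5. Share of normal sites in a pooled specificity denominator.** Assume one normal site per patient, all normal sites non-HSIL, and the 30% applied per lesion. For 150 patients:
- 1.5 lesions each: 150 / (150 + 0.70 × 225) = 150 / 307.5 = 48.8%.
- 2 lesions each: 150 / (150 + 0.70 × 300) = 150 / 360 = 41.7%.

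The shares are the same for 140 patients. HSIL prevalence among sampled sites, which drives NPV, would fall from 30% to 67.5/375 = 18% or 90/450 = 20%.

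**The case against.** **The 30% is a ceiling and the target is approximate.** This stands. Any loss up to 25% delivers 150, 140 is the worst case, and the plan sets no required half-width that 140 would breach. Section 9.2 also speaks of patients completing procedures in one clause and of evaluable images in the next. They are not the same thing, but the second is given as a reason for the inflation, so the two should agree.

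**Two biopsies each from 150 patients gives 300, the top of the stated range.** True, and the expectation of two or more is only stated as likely. But Section 5.1 attaches the range to 200 enrolled patients, and the range leaves no room for the normal sites on top of 1.5–2 lesions. Correcting it changes no stated half-width, because the table uses Section 9.2's counts.

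**Section 9.6 already includes the normal sites.** It says per biopsy twice, and normal sites are biopsied, so the natural reading is that they count. The single per-lesion phrase leaves some ambiguity. This is missing detail, not an arithmetic error.

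A reader might also infer three stronger things that the documents do not support:
- *That 200 means 150 + 50, leaving no allowance for loss.* Section 9.2 never says so. The undefined 50 is a matter of wording.
- *That more than two slides per patient makes the clustering allowance too optimistic.* At correlation 0.5 and 150 patients, the effective number, 150m / (1 + 0.5(m − 1)), is 180–200 for m = 1.5–2 and rises to 214–225 for m = 2.5–3. The table's correlated half-widths are already 1.5 times the independent ones (6.99/4.66).
- *That reported specificity will be biased.* The documents give no specificity by site type, so no bias can be shown.

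**Conclusion.** Two counts are wrong as written. Enrolling 200 yields 140 evaluable patients and 210–280 lesions at the stated maximum loss; 150 requires loss of 25% or less. Section 5.1's 225–300 is the lesion count for 150 patients attached to 200, and it omits the normal sites. With one normal site each, about 350–420 images (140 patients) or 375–450 (150 patients) should be expected, taking the median lesion number as the mean.

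The shortfall costs only about 0.3 points of half-width and does not make the study inadequate. Reporting specificity and NPV by site type is a worthwhile improvement rather than the correction of an error. Under the assumptions of step 5, normal sites would be about 42–49% of the pooled specificity denominator, so pooled specificity would differ from lesion specificity by that fraction of whatever gap exists between site types. The documents do not give that gap.

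**What to change.** - **Section 9.2:** state 140 evaluable patients and 210–280 lesions as the worst case at 30% loss, and give the half-widths for those counts. Restate the loss as 25% only if the sponsor can justify that rate; otherwise it merely fits the assumption to the total. If normal sites are counted, qualify the statement about slides per patient.
- **Section 5.1:** replace the image range with separate lesion and normal-site counts, and say whether they refer to enrolled or evaluable patients.
- **Section 5.1 and the Manual of Operations, step 19:** reconcile the two on the normal-site image and biopsy.
- **Section 9.6, Objective 1:** report per-biopsy specificity and NPV separately for Lugol's-negative and Lugol's-positive sites, as well as pooled.
- **Section 9.6, Objective 2b:** say who the 50 patients are and whether they fall within the 200.

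The cost is a few sentences and one stratified table. None of this needs extra patients or procedures.

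### The plan expects up to 30% of patients without evaluable mHRME images but gives no rule for counting them in SN, SP, PPV or NPV and plans no failure rate

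*Combined protocol and SAP*

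**What the plan says.** Section 9.2 states that "approximately 150 patients (225-300) lesions will be needed" for the precision targets, on the basis that "the median number of lesions per patient is approximately 1.5-2". It continues: "In order for 150 patients to complete study procedures, we will target a total enrollment of 200". Two reasons are given together: "because we will also be improving the technology as a secondary objective", and the authors "assume that up to 30% of patients may not have evaluable optimized HRME images".

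Section 5.1 expects 225-300 images from the 200 enrolled.

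Section 9.3 defines the population by eligibility alone. Section 9.5 lists SN, SP, PPV and NPV as primary, and efficiency and device development as secondary. Section 9.6 sets the SN and SP denominators by biopsy result and does not mention image evaluability. Under Objective 2a, biopsies averted is a percentage of HRA-visualized "lesions that the clinician originally categorized as potentially needing a biopsy". Objective 2b refers to a set of 50 patients that is not defined elsewhere.

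The procedure steps in Appendix 1 record the clinician's HRA read and plan for every abnormal area before the mHRME is inserted. At each site the image is then frozen once in focus, read and scored. Repeat images are allowed and the most representative one is kept. No step covers a site where no usable image is obtained.

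**The concern.** The device is meant to replace some tissue biopsies in real time. For that use, failing to produce a readable image is one of the test's outcomes: it spares no biopsy. If such sites drop out of the two-by-two table, the reported accuracy answers how good the read is when there is one. The primary objective concerns mHRME used during HRA, which is a wider question. The plan itself expects a loss that could reach 30% of patients, so the gap between the two answers could be large, and without a reported failure rate a reader could not reconstruct it. If the rule is chosen after the data are seen, the choice could also be influenced by the result.

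**Working it through.** **1. The plan's own sizing.** 150 × 1.5 = 225 and 150 × 2 = 300, which reproduces section 9.2. Section 5.1 gives the same 225-300 for all 200 enrolled, whereas 200 × 1.5 to 200 × 2 would be 300-400. The sizing therefore counts no images from the other 50 patients.

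The enrolment figure fits a 25% loss: 150 / 0.75 = 200. At the full 30%, 150 / 0.70 = 214.3, so 215 would be needed; 200 × 0.70 leaves 140 patients and 210-280 lesions. This is a side point, since the text says up to 30%.

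**2. Where a failed image would go.** SN and SP need an mHRME call and a histology result for each unit. A site with no readable image has only the second. Sections 9.3 and 9.6 neither exclude it nor assign it a call. With no assignment rule it falls out of the table by default.

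**3. Size of the effect (illustration).** Inputs:
- SN 93% and SP 87%, the preliminary anal HSIL figures in section 2.1, taken as the values among readable images.
- Failure share f = 10%, 20% and 30% of lesions, equal in HSIL and non-HSIL sites. This range is assumed; the documents give no failure rate for the final device, and their 30% is per patient.

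Formulas:
- SN, failures missed = 0.93 × (1 − f)
- SN, failures test-positive = 0.93 × (1 − f) + f
- SP, failures test-positive = 0.87 × (1 − f)

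| f | SN, missed | SN, test-positive | SP, test-positive |
|---|---|---|---|
| 0 | 93.0% | 93.0% | 87.0% |
| 10% | 83.7% | 93.7% | 78.3% |
| 20% | 74.4% | 94.4% | 69.6% |
| 30% | 65.1% | 95.1% | 60.9% |

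With the 94%/92% pilot figures in the opening summary instead, f = 10-30% gives SP 82.8% down to 64.4%, SN 84.6% down to 65.8% (missed), and SN 94.6% up to 95.8% (test-positive).

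**4. Predictive values under the test-positive rule,** applying the 30% HSIL prevalence of section 9.2 per lesion (an assumption), with the 93%/87% inputs:
- f = 0: PPV = 0.3 × 0.93 / (0.3 × 0.93 + 0.7 × 0.13) = 0.279 / 0.370 = 75.4%.
- f = 10%: 0.3 × 0.937 / (0.3 × 0.937 + 0.7 × 0.217) = 0.2811 / 0.4330 = 64.9%.
- f = 30%: 0.3 × 0.951 / (0.3 × 0.951 + 0.7 × 0.391) = 0.2853 / 0.5590 = 51.0%.
- NPV does not move: 0.609 / 0.630 = 96.7% at f = 0 and 0.4263 / 0.4410 = 96.7% at f = 30%, because no failure is called negative.

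**5. Against the planned precision.** SP shifts by 87.0 − 78.3 = 8.7 to 87.0 − 60.9 = 26.1 points. In the table of section 9.2, the 85% row at 225 slides has a half-width of 5.28 points (independence) or 7.93 (correlation 0.5). The unstated rule could move SP by more than the sampling error that the study was sized to control.

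**The case against.** The strongest reply is that the plan excludes nobody. Section 9.2 only inflates enrolment, section 9.3 defines the population by eligibility, and section 9.6 sets denominators by biopsy result. That is correct: a reader might infer a planned exclusion, but no sentence states one. What stands is that no rule is given, and a site without a read cannot enter the table unless one is.

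Four further points are fair:
- **Biopsies averted.** A reader might infer that this measure is also limited to successful images. The text does not support that. Its denominator is fixed at HRA, before imaging, so a lesion without a readable image already counts as not averted.
- **Sensitivity.** A reader might infer that SN must be overstated. If an unreadable site is treated as test-positive, SN does not fall (95.1% at 30%). The lower figures arise only if failures count as missed.
- **The 30%.** It is an upper limit per patient, tied partly to improving the technology. The 50 patients in Objective 2b equal 200 − 150, so much of the loss may be development patients, who may fairly be set aside. Repeat imaging may also keep the per-lesion rate well below 30%.
- **Non-random failure.** The documents name no causes of failed images. If failures are random, accuracy among readable images is unbiased for those images. The failure rate would still go unreported, and SP over all attempted lesions would still be lower under the test-positive rule.

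**Conclusion.** The point holds as an omission with a likely direction, not as a demonstrated bias. The sizing treats patients without evaluable images as replaceable, the analysis sections give no rule for them, and no failure rate is planned. Under the implied complete-case analysis, SN, SP, PPV and NPV describe readable images only.

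The measures most exposed are SP (87% among readable images against 61-78% over all attempted lesions) and, with it, PPV (75% against 51-65%). For SN the honest statement is a range set by the rule: 65-84% if failures are missed, 94-95% if they count as test-positive. NPV is unchanged under the test-positive rule.

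These figures assume 93%/87% among readable images, equal failure in HSIL and non-HSIL sites, a 10-30% failure range and, for PPV and NPV, 30% prevalence per lesion. The documents do not support reading the 30% as the failure rate of the final device; a lower rate would shrink every shift in proportion or nearly so.

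**What to change.** In sections 9.3 and 9.6, before results are seen:

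1. Define evaluable. Identify which patients were imaged with development versions and which with the final optimized device and software, state the point of change, and reconcile this with the 50 patients in Objective 2b.
2. Report the non-evaluable rate per lesion and per patient with a 95% CI, separately for the two phases.
3. For all lesions at which the final device was attempted, add an analysis that counts non-evaluable images as test-positive (biopsy not averted) for SP, PPV and NPV. Show SN with failures counted both as missed and as detected. Present this beside the evaluable-only analysis.
4. Confirm that the biopsies-averted denominator in Objective 2a stays all lesions first flagged at HRA, including those without a readable image.

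The cost is a few sentences and one extra table. It needs no further patients, readers or procedures. The documents set no point of change between development and final device, so the sponsor must state one, and the device version and any attempt without a usable image must be recorded for each site. The downside is a less favourable SP.
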